- **Assessment of rCBV and T2* signal intensity time curve**
 - **Quantification of the relative CBV** for differentiating tumor grade (off-site assessment)

The rCBV will be calculated on the CBV perfusion maps generated for each DSC-MRI perfusion. The regions of interest (ROIs) will be placed by off-site readers on the tumor for providing tumor CBV and also on normal tissue (contralateral normal-appearing white matter) for providing referenced CBV.

To be sure that the imaged tumor is the same as the tumor biopsied, results will be matched with the standard of truth for diagnosis of glioma grade. This standard of truth will be histopathological results collected on site (diagnosis based on 2021 WHO classification of Central Nervous System (CNS) tumors).

• **Evaluation of the T2* signal intensity time curve and assessment** (on-site and off-site assessments)

T2* signal intensity time curve will be visually assessed by on-site and off-site readers for the reliability of the curve in providing sufficient information for diagnosis purpose. The Full-Width at Half-Maximum (FWHM) and the maximum signal drop will be measured by off-site readers only.

Readers will record their confidence in diagnosis based on the reliability of the curve using a 5-point scale:

- 1 = nil: very uncertain
- 2 = poor: uncertain
- 3 = moderate: moderately certain
- 4 = high: good certainty
- 5 = excellent: very certain

- ***The following safety parameters will be assessed:***

- **Adverse events**, serious or not, related to IMP or not, that occur from the beginning of patient's participation in the trial (Informed Consent Form signature) until the end of the participation.

Statistical methods

Sample size:

The primary objective of the trial is to demonstrate the non-inferiority of DSC MRI perfusion using Elucirem® at 0.05 mmol/kg compared to Dotarem® at 0.1 mmol/kg in terms of diagnostic quality of the CBV perfusion map based on off-site evaluations.

A 12% non-inferiority margin was considered clinically as an unimportant difference and therefore relevant to establish acceptable diagnostic quality of Elucirem® relative to Dotarem®.

Statistical hypotheses

- H0: $p_{(\text{excellent+good for Elucirem}^{\circledR})} - p_{(\text{excellent+good for Dotarem}^{\circledR})} \leq -0.12$

- H1: $p_{(\text{excellent+good for Elucirem}^{\circledR})} - p_{(\text{excellent+good for Dotarem}^{\circledR})} > -0.12$

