7.2.2.1 Quantification of the relative CBV for differentiating tumor grade (off-site assessment)

For each DSC-MRI perfusion, the rCBV will be calculated on the generated CBV perfusion map. The regions of interest (ROIs) will be placed by off-site readers on the tumor for providing tumor CBV and also on normal tissue (contralateral normal-appearing white matter) for providing referenced CBV.

| | | |
|---|--|----------------------------|
|  CONFIDENTIAL | Protocol No. GDX-44-016 Version No. 1.0 - ITA Date 15 March 2023 | F015919-05 Page 30 / 59 |
|---|--|----------------------------|

To be sure that the imaged tumor is the same as the tumor biopsied, localization and size of the tumor assessed by the off-site readers will be matched with the standard of truth for grading gliomas. Standard of truth will be histopathological results collected on site (diagnosis based on 2021 WHO classification of CNS tumors).

7.2.2.2 Evaluation of the T2* signal intensity time curve and assessment (on-site and off-site assessment)

T2* signal intensity time curve will be visually assessed by on-site and off-site readers for the reliability of the curve in providing sufficient information for diagnosis purpose. If the curve is assessed as reliable, the full-width at half-maximum (FWHM) and the maximum signal drop will be measured by off-site readers only.

Readers will record their confidence in diagnosis based on the reliability of the curve using a 5-point scale:

- 1 = nil: very uncertain
- 2 = poor: uncertain
- 3 = moderate: moderately certain
- 4 = high: good certainty
- 5 = excellent: very certain

An overview of the imaging evaluation criteria to be assessed by the on-site reader (investigator (INV)) and the Independent Blinded Readers (IBR) is provided in the table below:

Table 2: Allocation of imaging evaluation criteria assessment per type of reader

| Evaluation criteria | Readers |
|--|---------|
| Technical adequacy of CBV map | IBR/INV |
| Diagnostic quality of CBV map | IBR/INV |
| r-CBV quantification | IBR |
| Visual assessment of T2* signal intensity time curve | IBR/INV |
| Maximum signal drop and FWHM T2* signal intensity time curve assessment | IBR |

7.2.3 *Recording of Adverse events*

Adverse events (AE), serious or not, related to IMP or not, that occur from the beginning of patient's participation in the trial (Informed Consent Form signature) will be recorded until the end of the participation (see [section 9.1.2](#)).

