The Mann-Whitney U-test will be used to test the difference in rCBV between the two trial arms by tumor grade categorization (high grade on one hand and low grade on the other hand) and between patients with high-grade and low-grade gliomas, within each of the two study arms at the significant level of 5%. The analysis will be performed for off-site readers.

Two analyses will be performed. The first one will consider the gliomas' grade categorization (high-grade versus low-grade) according to the stratification factor used at randomization, the second one will use the tumor grade categorization as per histological results (Standard of Truth) collected during the study.

Categorization as per histological results will be the following:

- Grade 1 and Grade 2 = Low grade,
- Grade 3 and Grade 4 = High grade.

The Benjamini-Hochberg method will be used to account for multiple testing.

Assessment and evaluation of the T2* signal intensity time curve (on-site and off-site assessment)

T2* signal intensity time curve will be visually assessed by on-site and off-site readers for the reliability of the curve in providing sufficient information for diagnosis purpose.

Number and percentage of patients for whom the reliability of the curve provides suffice information will be tabulated by trial arms.

For patients for whom the reliability of the curve provides suffice information, confidence in diagnosis will be presented for each arm using a 5-point scale:

- 1 = nil: very uncertain,
- 2 = poor: uncertain,
- 3 = moderate: moderately certain,
- 4 = high: good certainty,
- 5 = excellent: very certain.

Confidence in diagnosis will be summarized qualitatively and quantitatively by trial arm. The on-site and off-site read outcomes will be separately analyzed.

Assessment and evaluation of the T2* signal intensity time curve (off-site assessment)

Only for off-site readers, FWHM and the maximum signal drop will be compared between the trial arms using a Mann-Whitney U-test.

11.3.7 *Adverse Event*

All AEs will be coded using the MedDRA in force at the time of the data base lock.

An overall summary of AEs will be presented using the Screened Patient Set (SPS) to catch AEs of patients who did not receive trial drug that is to say Non-Treatment Emergent AEs (NTEAE). The table will be presented overall with the following variables:

- Total number of AEs.
- Total number of patients with at least one AE.

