2.2.2. Secondary efficacy Criteria

On-site Evaluation of CBV Map Diagnostic Quality

The same 4-point scale, described in [§2.2.1](#), is used to assess the diagnostic quality of CBV map generated by the **on-site readers**.

Quantification of the relative CBV for differentiating tumor grade (off-site assessment)

For each DSC-MRI perfusion, the rCBV will be calculated on the CBV perfusion map. The regions of interest (ROIs) will be placed by off-site readers on the tumors (i.e. lesions) for providing tumor CBV and on normal tissue (contralateral normal-appearing white matter) for providing referenced CBV.

Localization and size of the tumors assessed by the off-site readers will be compared to the targeted tumor concerned by the standard of truth for grading gliomas in order to check if there is a correspondence between SOT tumor and one of the tumors assessed by the off-site readers. Standard of truth will be the histopathological results collected on site (diagnosis based on the 2021 WHO classification of CNS tumors).

Assessment and evaluation of the T2* signal intensity time curve (on-site and off-site assessment)

T2* signal intensity time curve will be visually assessed by on-site and off-site readers for the reliability of the curve in providing sufficient information for diagnosis purpose. If the curve is assessed as reliable, the full-width at half-maximum (FWHM) and the maximum signal drop will be measured by off-site readers only.

Readers will record their confidence in diagnosis based on the reliability of the curve using a 5-point scale:

- 1 = nil: very uncertain
- 2 = poor: uncertain
- 3 = moderate: moderately certain
- 4 = high: good certainty
- 5 = excellent: very certain

The rCBV, T2* signal intensity, FWHM and maximum signal drop will be assessed at lesion level. Analyses relative to rCBV will be performed at patient or patient / reader level and analyses relative to T2* signal intensity, FWHM and maximum signal drop will be performed at lesion or lesion / reader level. Of note, analyses for on-site reader at patient level are equivalent to lesion level as only one lesion is considered.

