Assessment and evaluation of the T2* signal intensity time curve at lesion level (on-site and off-site assessment)

T2* signal intensity time curve will be visually assessed by on-site and off-site readers for the reliability of the curve in providing sufficient information for diagnosis purpose.

For on-site assessment, the number and percentage of lesions for whom the reliability of the curve provides suffice information will be tabulated by trial arms.

For the off-site assessment, the number and percentage of lesions for whom the reliability of the curve provides suffice information will be tabulated by trial arms.

CONFIDENTIAL	STATISTICAL ANALYSIS PLAN N° GDX-44-016 VERSION N° 4.0 (REF I011622)	F015830-03 Page 26 / 35
--------------	--	----------------------------

For lesions for whom the reliability of the curve provides suffice information, confidence in diagnosis will be presented, for each arm, by on-site readers and for the off-site assessment for each off-site reader, using a 5-point scale:

- 1 = nil: very uncertain,
- 2 = poor: uncertain,
- 3 = moderate: moderately certain,
- 4 = high: good certainty,
- 5 = excellent: very certain.

Confidence in diagnosis will be summarized qualitatively and quantitatively by trial arm. The on-site and off-site read outcomes will be separately analyzed.

For the overall reliability of the T2* signal intensity time curve taking into account the consensus decision, the worst confidence in diagnosis between the two readers will be considered if no consensus decision was needed (worst case scenario).

Assessment and evaluation of the T2* signal intensity time curve (off-site assessment)

Only for off-site readers, FWHM and the maximum signal drop will be tabulated at lesion level by off-site reader and compared between the trial arms using a Mann-Whitney U-test.

For the overall FWHM taking into account the consensus decision, the mean of values between the two readers for each lesion will be considered if no consensus decision was needed.

For the overall maximum signal drop taking into account the consensus decision, the maximum of values between the two readers for each lesion will be considered if no consensus decision was needed.

If the curve is not reliable, no calculation of FWHM and the maximum signal drop will be performed.

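### Diagnostic confidence, FWHM and signal drop are analysed only for curves judged reliable, so the arm comparison rests on post-randomisation selection; confidence should also be shown for all assessed lesions

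*SAP*

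**What the plan says.** SAP 5.5.3 first has readers judge whether each T2* curve is reliable enough for diagnosis, and reports that result by arm: "the number and percentage of lesions for whom the reliability of the curve provides suffice information will be tabulated by trial arms". Confidence is then restricted: "For lesions for whom the reliability of the curve provides suffice information, confidence in diagnosis will be presented". The restricted scores are described without a test: "Confidence in diagnosis will be summarized qualitatively and quantitatively by trial arm". For the two measured quantities the SAP states: "If the curve is not reliable, no calculation of FWHM and the maximum signal drop will be performed". The values that remain are compared between arms with a Mann-Whitney test.

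The protocol body agrees. Section 7.2.2.2 has "If the curve is assessed as reliable, the full-width at half-maximum (FWHM) and the maximum signal drop will be measured by off-site readers only", and section 11.3.6.2 has "For patients for whom the reliability of the curve provides suffice information, confidence in diagnosis will be presented for each arm".

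Two places read differently. The protocol synopsis puts no reliability condition on measurement ("The Full-Width at Half-Maximum (FWHM) and the maximum signal drop will be measured by off-site readers only"), nor on its planned comparisons or its confidence summary. SAP 2.2.2 words the recording of confidence without a condition: "Readers will record their confidence in diagnosis based on the reliability of the curve using a 5-point scale". Scores for unreliable curves may therefore exist and simply go unsummarised.

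**The concern.** Whether a curve is reliable is itself a result of the examination. It is judged after randomisation and injection, and the agent can influence it. Keeping only reliable curves therefore compares subsets that randomisation did not create.

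This bears hardest on confidence. The third secondary objective (Protocol 2.2, SAP 1.1.2) is to assess curve reliability through diagnostic confidence. The scale has a bottom category for very uncertain readings, yet the curves most likely to earn it are taken out before the scale is summarised. If unreliable curves would score lower than reliable ones, confidence is overstated within each arm, and by more in whichever arm loses more curves. On-site, the reader deciding which curves count also knows the agent (Protocol 5.3.2).

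Nothing in the plan measures the effect. SAP 5.5.2 (sensitivity analyses) and SAP 3.5 (missing data) are both marked not applicable.

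**Working it through.** **The plan's own figures.** No figure is given for the T2* analyses: no expected share of reliable curves, no effect size, no reliability threshold. The only sizing is for the primary endpoint (SAP 3.3), and it reproduces. n per arm = (1.960 + 0.842)² × (2 × 0.94 × 0.06) / 0.12² = 61.5, rounded up to 62; 124 / 0.90 = 137.8, rounded up to 138. I use 62 per arm below, with one lesion per patient. All rates, means and shifts are assumptions.

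**Confidence.** Let u be the share of unreliable curves and m the mean confidence among reliable ones. With unreliable curves counted as 1, the all-lesion mean is (1 − u) × m + u × 1. Differences are reference minus test.

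| u ref / test | m ref / test | All-lesion means | All-lesion difference | Reliable-only difference |
|---|---|---|---|---|
| 5% / 5% | 4.2 / 4.2 | 4.04 / 4.04 | 0.00 | 0.00 |
| 5% / 10% | 4.2 / 4.2 | 4.04 / 3.88 | 0.16 | 0.00 |
| 5% / 15% | 4.2 / 4.2 | 4.04 / 3.72 | 0.32 | 0.00 |
| 5% / 20% | 4.2 / 4.2 | 4.04 / 3.56 | 0.48 | 0.00 |
| 5% / 5% | 4.2 / 4.0 | 4.04 / 3.85 | 0.19 | 0.20 |
| 15% / 5% | 4.2 / 4.0 | 3.72 / 3.85 | −0.13 | +0.20 |

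The fourth row written out: 0.95 × 4.2 + 0.05 = 4.04; 0.80 × 4.2 + 0.20 = 3.56; difference 0.48. The restricted summary can hide a difference, leave it almost unchanged, or reverse its sign.

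**FWHM and signal drop.** The answer depends on how unreliability relates to the measured value. Take a true shift of 0.5 SD.

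- *Reliability is a cut-off c on the value itself.* The mean among reliable curves is μ + φ(a) / (1 − Φ(a)), with a = c − μ in SD units. For c = −1.645, the reference arm (μ = 0) keeps 95% with mean 0.109, and the test arm (μ = −0.5) keeps 87% with mean −0.263. The difference is 0.37 SD. Cut-offs keeping 90% versus 78%, or 80% versus 63%, give 0.32 and 0.26 SD. In 3,000 simulated trials, Mann-Whitney power was about 76% with every curve measured, against 61% at the 95% cut-off and 34% at the 80% cut-off.
- *Reliability is unrelated to the value.* The difference is not attenuated. Power falls only through smaller numbers: about 76% to 74% with 5% lost per arm, and 77% to 67% with 20% lost.
- *Both arms lose 10% at a common low value.* The all-curve difference is 0.9 × 0.5 = 0.45 SD, and the reliable-only difference is 0.50 SD, which is larger.

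**The case against.** The strongest defence is that the loss is disclosed. The share of reliable curves is tabulated by arm for both types of reader. Tables 14.2.2.27 to 14.2.2.34 put reliability and confidence together, and Listings 16.2.6.5 to 16.2.6.7 give individual values. A careful reader could add the unreliable curves to the low-confidence ones. This stands, and it limits the harm. It does not supply the combined summary, or an interval for the difference in reliability.

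Second, confidence has no between-arm test and the third objective names Elucirem alone, so no formal inference on confidence is distorted. That is correct. Only FWHM and signal drop are tested.

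Third, declining to measure a curve that cannot be interpreted is reasonable. That also stands: the FWHM and signal-drop rule needs a label, not removal.

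A reader might infer more: that the restriction systematically shrinks differences and pulls the tests towards no difference. The documents do not support this. Attenuation needs reliability to track the measured value and one arm to lose more curves. Reliability is a visual judgement with no stated signal-drop threshold, and technically non-diagnostic maps have already been removed (SAP 2.2). A reader might also want unreliable curves ranked worst in the main tests. For FWHM the documents define no worse direction. For signal drop, worst-ranking would change what is being estimated.

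**Conclusion.** The point holds as a minor one. All three measures are conditional on a post-randomisation judgement, and the bias in the arm comparison can be nil, towards zero, away from zero, or large enough to change the sign. No single direction can be claimed, and the simulated power losses apply only under the cut-off mechanism. The substantive weakness is in confidence, where the planned summary leaves out the cases the objective is about. The size of 0.48 points against 0.00 rests on assumed rates of 5% versus 20% unreliable, an assumed mean of 4.2 among reliable curves in both arms, and a score of 1 for each unreliable curve. With equal 5% rates and equal means the two summaries agree on the difference. The non-inferiority analysis is unaffected.

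**What to change.** 1. Tabulate confidence by arm over all assessed lesions. Use the reader's recorded score where one exists for an unreliable curve; otherwise count the curve in the lowest category. Keep the reliable-only table as secondary.
2. Report the between-arm difference in the proportion of reliable curves with a 95% CI.
3. Label the FWHM and signal-drop tests as conditional on a reliable curve, to be read beside that proportion. A worst-rank analysis of signal drop may be added as a sensitivity analysis only, with none for FWHM.
4. Reconcile the protocol synopsis, which states no reliability condition, with Protocol 7.2.2.2 and 11.3.6.2 and with the SAP.

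The cost is one extra set of tables and matching wording in both documents, since the rule is in the protocol body as well as the SAP. No new data collection is needed.

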1 INTRODUCTION

1.1 Trial Rationale

Gliomas are the most common primary intracranial tumors, representing 81% of malignant brain tumors [1]. They are considered the most rapidly growing malignancies of the central nervous system, with glioblastoma comprising more than 50% of all gliomas. Early and accurate tumor diagnosis and classification is essential for patient care management, as treatment modalities will significantly differ according to the glioma grade.

Perfusion MRI provides additional information to conventional MRI [2]. This MRI technique can be used to image neovascularization, a hallmark of tumor progression. In this way, perfusion MRI helps to characterize brain gliomas [3]. Perfusion MRI sequence is implemented in the standard imaging protocol of a large number of sites in USA and in Europe [4; 5]. Among MRI perfusion techniques, Dynamic Susceptibility Contrast MRI is the most used perfusion method.

DSC-MRI is a technique in which the first pass of a bolus of GBCA through brain tissue is monitored by a series of T2- or T2*-weighted MR images [6]. The susceptibility effect of the paramagnetic contrast agent leads to a signal loss in the signal intensity-time curve. Using a signal model for susceptibility contrast, the signal information can be converted into a contrast medium concentration -time curve on a voxel-by-voxel basis. Various hemodynamic parameters can be calculated from the concentration-time curve. Among them, relative CBV (rCBV) is the most used parameters. The ratio of rCBV in lesions and in contralateral normal-appearing white matter is often calculated for quantification. It is commonly accepted that CBV reflects tumor neoangiogenesis and correlates with glioma grade [7]. Glioblastoma presents with elevated rCBV due to increased cellular proliferation.

Most DSC perfusion studies are performed using GBCA at 0.1 mmol/kg. Yet there are several reasons for considering reduction of GBCA dose for brain DSC perfusion. The main reasons are safety concerns such as the development of Nephrogenic Systemic Fibrosis (NSF) in at-risk subjects with impaired renal function [8; 9] and the potential retention of gadolinium in tissues even in subjects with normal renal function [10-15].

In the context of the necessity to perform multiple contrast-enhanced MR imaging applications, the use of half dose of gadolinium is to be considered.

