8.2 Imaging Characteristics

8.2.1 *Equipment*

The imaging procedures will be performed using a MRI scanner, equipped with echo-planar imaging capabilities, that can perform the required sequences.

MRI units with 1.5T or 3T magnetic field will be used regardless of the manufacturer. The following information must be recorded: the manufacturer and field strength of the MRI device.

8.2.2 *Imaging protocol*

The same parameters setting for the same sequence should be used for unenhanced images and for contrast-enhanced images in each patient.

The required sequences and parameters per patient for Elucirem® and Dotarem® should be as similar as possible. Details on required sequence and parameters will be provided in the Imaging Manual.

Brain imaging protocol will include:

Unenhanced sequences:

- Axial 3D T1WI GRE
- Axial 2D T2WI T(F)SE
- Axial 2D FLAIR

Contrast-enhanced sequences:

- Perfusion imaging: Axial DSC T2* EPI
- Axial 3D T1WI GRE

It is not allowed to add any sequence between contrast agent injection and perfusion imaging.

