2.1.7. MRI examination

MRI examination parameters are:

- manufacturer of the MRI machine,
- magnetic field strength (in Tesla),
- Pre-injection Axial 3D T1 weighted GRE sequence performed,
- Pre-injection Axial 2D T2 weighted T(F)SE sequence performed,
- Pre-injection Axial 2D Flair sequence performed,
- Post-injection Axial DSC T2* perfusion sequence performed,
- Post-injection Axial 3D T1 weighted GRE sequence performed.

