3.4. Adjustment for covariates

Not Applicable.

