5.4.7. MRI examination

All the sequences performed during the MRI examination as well as the magnetic field strength (in Tesla) will be tabulated by arm.

Listing of MRI examinations will be presented in CSR Appendix 16.2.4.

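### Maximum signal drop, and less clearly FWHM, may depend on 1.5T versus 3T, yet the arm comparison is unstratified and has no confidence interval (optional improvement)

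*SAP*

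**What the plan says.** Protocol 8.2.1 accepts both field strengths: "MRI units with 1.5T or 3T magnetic field will be used regardless of the manufacturer". It then requires that the information be kept: "The following information must be recorded: the manufacturer and field strength of the MRI device". SAP 2.1.7 lists field strength among the MRI examination parameters. Its only planned use is descriptive (SAP 5.4.7): "All the sequences performed during the MRI examination as well as the magnetic field strength (in Tesla) will be tabulated by arm".

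For the curve measurements, SAP 5.5.3 plans that "FWHM and the maximum signal drop will be tabulated at lesion level by off-site reader and compared between the trial arms", with a Mann-Whitney U-test. Protocol 11.3.6.2 names the same test. No strata are mentioned. SAP 3.4 (covariates) and SAP 3.11 (subgroups) are both marked as not applicable. Randomisation is stratified by low versus high glioma grade and nothing else (SAP 1.2). Tables 14.2.2.35 to 14.2.2.38 show the two measures by arm, and by arm and grade, but not by field strength. The standard summaries of SAP 3.1 (n, mean, SD, minimum, median, maximum) will be given by arm. No estimate of the arm difference with a confidence interval is planned.

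**The concern.** Maximum signal drop measures the size of a physical effect. Protocol 1.1 says: "The susceptibility effect of the paramagnetic contrast agent leads to a signal loss in the signal intensity-time curve". A susceptibility effect can plausibly differ between 1.5T and 3T. That sentence supports field dependence for signal drop more than for FWHM, which is a width of the curve and not a depth.

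In a parallel-group trial each patient is scanned with one agent only, so differences between scanners enter the arm comparison directly. Two things can follow if field strength matters. The spread between field strengths adds noise and can hide a real difference between half-dose Elucirem and full-dose Dotarem. And if one arm happens to have more 3T scans, part of the observed difference belongs to the scanner.

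Protocol 1.1 aims to show that the two products are equally efficient for qualitative and quantitative perfusion evaluation. A non-significant p-value without an interval is easily read as similarity, so lost power and a missing interval both lean towards that reading.

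**Working it through.** **1. The plan's own figure.** The only power statement concerns the primary endpoint (SAP 3.3).
- n per arm = (1.960 + 0.842)² × 2 × 0.94 × 0.06 / 0.12² = 61.5, so 62.
- Power at 62 = Φ(0.12 / √(2 × 0.94 × 0.06 / 62) − 1.96) = 80.3%.
- 124 / 0.9 = 137.8, so 138.

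All three reproduce. The documents state no power, SD or effect size for FWHM or maximum signal drop.

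**2. Power with and without stratification.** Taken from the documents: 62 per arm, 1:1 allocation, two-sided 5%. Assumed, because the documents are silent: one value per patient, normal errors within each field strength, an arm effect of 0.52 within-field SD (chosen to give about 80% power when field has no effect), a 3T shift of 0 to 1.5 SD, and a minority field share of 20%, 30% or 50%. There were 5,000 runs per cell, so each figure has a simulation standard error of about √(0.8 × 0.2 / 5000) = 0.6 points. Entries are power in per cent, plain Mann-Whitney / van Elteren.

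| Field shift (SD) | 50% share | 30% share | 20% share |
|---|---|---|---|
| 0 | 79.8 / 78.9 | 79.9 / 78.8 | 80.6 / 80.0 |
| 0.25 | 78.5 / 78.3 | 79.5 / 79.5 | 78.3 / 78.1 |
| 0.5 | 77.4 / 79.0 | 77.7 / 78.6 | 78.3 / 79.2 |
| 1.0 | 71.3 / 80.6 | 71.5 / 78.9 | 74.1 / 79.4 |
| 1.5 | 58.7 / 79.0 | 63.9 / 79.9 | 68.3 / 80.3 |

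Ranks taken within strata do not change when one stratum is shifted, so the true power of the stratified test does not depend on the field shift. Its column varies around 79% through simulation error alone. The loss from pooling is therefore nil up to 0.25 SD and about 1-2 points at 0.5 SD. It is about 5-9 points at 1 SD and about 11-20 points at 1.5 SD (79 − 68 = 11; 79 − 59 = 20). With no field effect, stratifying costs about one point.

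A second simulation, with an arm effect of 0.50 SD and a 50:50 mix, gave the same pattern: 76 / 75 with no shift, 74 / 75 at 0.5 SD, 66 / 75 at 1 SD and 55 / 75 at 1.5 SD.

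**3. Overall type I error.** With no arm effect, the plain test rejected in 4.1% to 5.6% of runs and the stratified test in 4.4% to 5.9% (2,500 runs per cell). Both are near 5%.

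**4. Chance imbalance.** The SD of the between-arm difference in 3T share is √(2 × 0.5 × 0.5 / 62) = 9.0 points at a 50% share and √(2 × 0.3 × 0.7 / 62) = 8.2 points at 30%. By the normal approximation, a gap of 10 points or more has probability 27% (22% at a 30% share). A gap of 15 points or more has probability 9% (7%).

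A gap shifts the mean arm difference by gap × field shift. With 26 versus 36 of 62 scans at 3T, the gap is 10/62 = 0.16, which gives 0.08, 0.16 or 0.24 SD for field shifts of 0.5, 1 or 1.5 SD.

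Conditional on a gap of about 15 points (26 versus 36, or 14 versus 23 at a 30% share), the plain test rejects a true null in about 5-6%, 9-10% and 11-13% of runs for those three shifts. The stratified test stays at about 5-6%. With a gap of about 10 points, the plain test is still at 5-6%.

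**The case against.** The strongest reply is that the harm rests on a field effect that no passage gives. Protocol 1.1 ties signal loss to the contrast agent and does not mention field strength. At 0.5 SD the gain from stratifying is 1-2 points, within what many would call a matter of preference. This stands: it makes the conclusion conditional and holds the severity down.

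Several stronger readings are tempting, but the documents do not support them:
- **The test is invalid, or its error rate is inflated.** It is not. Under randomisation the overall level stays near 5%. Only the error conditional on a realised imbalance moves, and SAP 5.4.7 would make that imbalance visible by arm.
- **The test certainly loses power.** Only if field strength shifts the measure by roughly 0.5 SD or more.
- **FWHM is affected as signal drop is.** Nothing in the documents ties curve width to field strength.
- **Field strength is fixed by the site.** The documents do not say so. They say only that either field strength may be used and must be recorded.
- **Only a p-value is planned.** Summaries by arm are planned, so a crude difference can be read off. What is missing is its confidence interval.

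It is also fair that the simulation differs from the planned analysis. The plan works at lesion level and only on reliable curves, so numbers may differ from 62 per arm, and several lesions from one patient are not independent. The powers above show the direction and rough size of the effect and are not the power of the planned test. Finally, field strength is one of several recorded acquisition variables (manufacturer, injection rate and preload bolus are others), and the documents do not rank them.

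**Conclusion.** The point holds in a limited, conditional form. A variable that must be recorded, and that plausibly bears on maximum signal drop, is left out of the between-arm test, and no interval for the arm difference is planned. Under the assumptions stated, pooling costs nothing at a field shift of 0.25 SD or less, and 20 points of power at most at 1.5 SD with an even field mix. Where the trial falls in that range cannot be told from the documents. The case is weaker for FWHM.

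Severity is low and the change optional. The comparisons sit under supplementary analyses in SAP 5.5.3. The T2* curve objective is framed as reliability and diagnostic confidence, and the primary non-inferiority conclusion does not depend on them.

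**What to change.** In SAP 5.5.3, replace the plain test with a van Elteren (stratified Wilcoxon) test by field strength (1.5T, 3T) for maximum signal drop, and for FWHM for consistency. Report the Hodges-Lehmann shift between arms, combined across the two strata, with its 95% CI. Amend SAP 3.4 so that it no longer excludes this.

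The change should be made before results by arm are seen. All parties except the off-site readers are open (Protocol 5.3.2), so an adjustment chosen after looking at the field-strength table would be data-driven. If it is too late, report the stratified result as a labelled supplementary analysis beside the planned test.

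The cost is a few lines of SAP text and SAS code, no new data, and about one point of power if field strength has no effect. The change does not deal with several lesions from one patient; that needs its own solution.
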